**10) Interventions:**

Number of Arms: 4

Allocation: Randomized

Enrollment Type: Anticipated

Number of Subjects: 80 participants with subclinical depression

Arm 1: Control

Arm Title: Priming sham TBS – followed by iTBS after an ISI of 0 minutes

Arm Description: self-explanatory, see Arm Title

Arm 2: Experimental

Arm Title: Priming cTBS – followed by iTBS after an ISI of 0 minutes

Arm Description: self-explanatory, see Arm Title

Arm 3: Experimental

Arm Title: Priming cTBS – followed by iTBS after an ISI of 10 minutes

Arm Description: self-explanatory, see Arm Title

Arm 4: Experimental

Arm Title: Priming cTBS – followed by iTBS after an ISI of 20 minutes

Arm Description: self-explanatory, see Arm Title

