## **11) Outcome Measures:**

### **Outcome 1: Primary Outcome Measure**

Title: HbO during rest before and after stimulation (raw values and change scores)

Description: Prefrontal neural activity will be measured using fNIRS before (baseline) and about 10-15 minutes after the stimulation (delay will be recorded). TBS-induced blood oxygen changes (HbO) at rest will be evaluated in the frontal cortex

Time Frame: baseline, post intervention

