## **13) Statistical Analysis Plan:**

fNIRS data analysis will follow the standard processing steps. This includes spatial registration (recording of standard cranial landmarks nasion, inion, left and right ear, and the 3D locations of the fNIRS probes); transformation to MNI space [39]; band-pass

filtering for motion artifact removal; and estimation of the hemodynamic response function using GLM, as implemented in the NIRS Toolbox for MATLAB. Comparisons between baseline and task HbO will reveal task-related de/activations, corrected for multiple comparisons (52 channels). Average HbO changes will then be determined for each channel and each measurement and entered into second-level analysis. Similarly, means of HbO for pre and post-stimulation will be entered into second-level analysis.

A t-test between pre- and post-stimulation in condition 1 will be performed to test hypothesis 1. Hypothesis 1 will be supported if there is a significant increase in prefrontal HbO after stimulation.

A t-test between condition 2 and 1 using change scores will be performed to test hypothesis 2. Hypothesis 2 will be supported if there is a significant stronger change in HbO in condition 1 compared to condition 2

A t-test between condition 3 and 1 using change scores will be performed to test hypothesis 3. Hypothesis 3 will be supported if there is a significant stronger change in HbO in condition 3 compared to condition 1.

A t-test between pre- and post-stimulation in condition 4 and between change scores of condition 1 and 4 will be performed to test hypothesis 4. Hypothesis 4 will be supported if there is a significant increase in prefrontal HbO after stimulation, but no significant difference in change scores between condition 1 and 4.

Regarding the three exploratory hypotheses about participants' behavior (reaction times, hits and misses) and HbO changes during cognitive tasks, linear mixed models will be conducted to determine differences between conditions, followed by post-hoc pairwise comparisons. Here, a three-way interaction between time, condition and emotion will be evaluated and followed by post-hoc two-way interactions and pairwise comparisons.

Hypothesis E1 will be supported if there is a significant change in HbO and/or behavioral measures in condition 1 in some (e.g. sad) but not other emotions (e.g. happy) after stimulation (following a post-hoc 2-way interaction between time and emotion).

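### The between-arm tests of resting HbO (H2, H3 and part of H4) use unadjusted change scores; they are valid, but adjusting for the baseline already measured would make them more precise

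*Combined protocol and SAP*

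**What the plan says.** Outcome 1 (section 11) is titled "HbO during rest before and after stimulation (raw values and change scores". Its description sets the timing: "Prefrontal neural activity will be measured using fNIRS before (baseline) and about 10-15 minutes after the stimulation (delay will be recorded". A baseline resting value is therefore planned for every participant.

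Section 13 then names the between-arm tests:

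- Hypothesis 2: "A t-test between condition 2 and 1 using change scores will be performed to test hypothesis 2".
- Hypothesis 3: "A t-test between condition 3 and 1 using change scores will be performed to test hypothesis 3".
- Hypothesis 4: "A t-test between pre- and post-stimulation in condition 4 and between change scores of condition 1 and 4 will be performed to test hypothesis 4". Only the second part of this is a between-arm comparison.

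No covariate is named for any of them. Modelling appears only for the exploratory hypotheses on task HbO and behaviour, where "linear mixed models will be conducted to determine differences between conditions, followed by post-hoc pairwise comparisons". Section 13 also sends pre- and post-stimulation means to a second-level analysis, but does not say that this analysis adjusts for baseline.

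Section 10 gives "Number of Subjects: 80 participants with subclinical depression" and "Number of Arms: 4", with randomised allocation. It states no allocation ratio. Section 13 sets alpha at 0.05 with Bonferroni-Holm adjustment.

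**The concern.** These contrasts carry the first objective, which is how the interval between priming and test stimulation changes the effect on resting HbO.

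Subtracting baseline fixes the pre-post slope at 1. When pre and post SDs are equal, the true slope is r, which is below 1. The change score then over-corrects, with two consequences. Baseline noise is added to the outcome. And an arm that happens to start high tends to show a smaller change through regression to the mean, so a chance baseline difference passes into the estimated effect with its sign reversed.

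With about 20 participants per arm, and no power calculation in the documents, lost precision is not shown to be affordable. It also matters for hypothesis 4, which counts a non-significant difference between conditions 1 and 4 as support. A noisier comparison makes that result easier to reach.

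**Working it through.** The documents state no power, SD or effect size, so there is no planned figure to reproduce.

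**Inputs**

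- 80 participants and 4 arms (section 10). 80/4 = 20 per arm assumes equal allocation.
- Alpha 0.05 with Bonferroni-Holm (section 13). Two-sided testing is assumed.
- Pre-post correlation r of resting HbO: not given, so a range is shown.
- Assumed: equal pre and post SD, set to 1, and a true difference of 0.8 SD for the power figures.

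**Variance of a two-arm contrast, n per arm**

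- Change score: 2(1−r) × 2/n.
- Baseline-adjusted, large sample: (1−r²) × 2/n.
- Ratio: (1−r²) / [2(1−r)] = (1+r)/2, so the reduction is (1−r)/2.

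Estimating the slope costs a little. The expected inflation is 1 + 1/(within-arm df − 2). That is 1 + 1/36 for a two-arm model (38 df) and 1 + 1/74 for a four-arm model (76 df). The net reduction is 1 − (1+r)/2 × inflation:

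| r | Large sample | Net, four-arm | Net, two-arm |
|---|---|---|---|
| 0.3 | 35% | 34.1% | 33.2% |
| 0.5 | 25% | 24.0% | 22.9% |
| 0.7 | 15% | 13.9% | 12.6% |
| 0.9 | 5% | 3.7% | 2.4% |
| 0.95 | 2.5% | 1.2% | −0.2% |

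Simulation of the two-arm model (20,000 trials per r) gave reductions of 34%, 23%, 13%, 2% and 0% in the same order.

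**Power for a 0.8 SD difference**, simulated, change-score t-test v four-arm adjusted model with pooled variance:

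| r | At 0.05 | At 0.0125 |
|---|---|---|
| 0.3 | 55% v 75% | 34% v 54% |
| 0.5 | 70% v 81% | 47% v 64% |
| 0.7 | 89% v 94% | 73% v 83% |

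The 0.0125 column is the first Holm step, 0.05/4, if the family is four tests. The family size is an assumption. A two-arm adjusted model gains slightly less. By the noncentral t at 0.05, power is 54.9% v 72.2%, 69.3% v 80.1% and 88.9% v 92.5% at r = 0.3, 0.5 and 0.7.

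**Chance imbalance**

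- SD of the baseline difference between two arms: √(2/20) = 0.316 SD.
- P(difference exceeds 0.5 SD in either direction): 0.5/0.316 = 1.58, which gives 0.114.
- Bias of the change-score contrast given the observed imbalance: −(1−r) × imbalance.
- Imbalance of 0.316 SD: a shift of 0.3 × 0.316 = 0.09 SD at r=0.7, and 0.7 × 0.316 = 0.22 SD at r=0.3.
- Imbalance of 0.5 SD at r=0.5: a shift of 0.25 SD.

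Averaged over randomisation, the shift is zero. The simulated mean error of the change-score contrast was within 0.003 SD of zero at every r tried.

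**Unequal variances.** If condition 3 has 1.5 times the residual SD of the other arms (an assumption), a four-arm model with pooled variance has a simulated type I error of about 8% for 3 v 1. A two-arm adjusted model has about 5.5%, and the two-arm t-test about 5%.

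**The case against.** The strongest reply is that nothing here is an error. Allocation is randomised, the change-score t-test holds its type I error at about 5%, and its standard error already covers chance imbalance. That stands. A reader might infer that the planned tests are biased or invalid, but the documents do not support this: the bias exists only conditionally on an observed imbalance and averages to zero.

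A reader might also take a saving of 15–35% as a property of this trial. It is not. That range is (1−r)/2 for r between 0.7 and 0.3, and the documents give no r. Both recordings come from the same person around one stimulation procedure, so a high r cannot be excluded. At r=0.9 almost nothing is gained.

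Nor is adjustment free in every form. The plan expects priming to abolish, strengthen or leave unchanged the response in different arms, so unequal variability is plausible. A pooled four-arm model could then exceed its nominal error rate, which is why the fix specifies robust errors or two-arm models.

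A reader might conclude that Outcome 1 must be redefined and change scores dropped. That is unnecessary. Regressing change on condition and baseline gives the same condition contrast as regressing the post value, and the within-arm tests still need the change.

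Finally, section 3 refers detail to a separate proposal that was not supplied. That does not alter the change-score t-tests that section 13 states outright.

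**Conclusion.** The point holds as a matter of efficiency. H2, H3 and the between-arm part of H4 are valid tests that leave collected information unused and do not correct for the baseline imbalance that actually occurs. With 20 per arm and equal pre and post SDs, adjustment would reduce the variance of each contrast by about a third at r=0.3, a quarter at r=0.5, a seventh at r=0.7 and very little at r=0.9. For a 0.8 SD effect that is about 5 to 20 percentage points of power at 0.05, and 10 to 20 at 0.0125, over r from 0.7 to 0.3. The direction of the gain is secure unless r is close to 1; its size is not known from the documents. Better precision eases the reliance of H4 on a non-significant difference but does not cure it. The change is worth making, and best made before outcome data are seen.

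**What to change.** In section 13, replace the between-arm t-tests for H2, H3 and the second part of H4 with a linear model of resting HbO on condition, with baseline resting HbO as covariate, and planned contrasts 2 v 1, 3 v 1 and 4 v 1. The response may be the post-stimulation value or the change, since the contrasts are identical. Either fit one four-arm model with heteroscedasticity-robust standard errors, in a small-sample form such as HC3, or fit a separate two-arm model for each contrast. Keep the planned Bonferroni-Holm adjustment.

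Leave Outcome 1, H1 and the within-arm part of H4 as written. Keep the change-score t-tests as a sensitivity analysis.

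The cost is revised wording in the plan, one degree of freedom for the slope and a little more analysis work. No extra measurement is needed. If r proves very high the gain will be negligible; at r=0.95 a two-arm model roughly breaks even.

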## **2) Brief Summary:**

Priming stimulation is a highly promising tool to boost the beneficial effects of therapeutic repetitive transcranial magnetic stimulation (rTMS) in psychiatry. The potentiating effects of priming stimulation, however, depend on the time interval between the priming and the test stimulation. Although it is known that too short and too long intervals have no effects, systematic studies that identify the time needed to maximize efficacy have not yet been done. Thus, there is a need for studies to investigate the effects of priming stimulation in order to fully utilize the potential benefits and advantages of this promising new rTMS protocol. Here we propose a research program that will systematically investigate the neuromodulatory process underlying priming stimulation to enhance metaplasticity in the left dorsolateral prefrontal cortex (DLPFC) – one of the main targets for therapeutic rTMS – in individuals with subclinical depression.

The brain is a highly plastic organ and its activity can be influenced using rTMS. At the same time, the brain also has a mechanism – called homeostatic metaplasticity – which counteracts extreme plastic changes. Homeostatic metaplasticity therefore can limit the beneficial effects of brain stimulation interventions. However, priming stimulation protocols that include both a priming and a test stimulation session may utilize homeostatic metaplasticity to increase the beneficial effects of brain stimulation, although the optimal treatment parameters for priming are not known. Moreover, little is known about homeostatic metaplasticity in the DLPFC, an area that is particularly relevant for psychiatric conditions given its role in the top-down control of emotions. Here, we will systematically study metaplasticity using priming theta-burst stimulation (TBS), a potent form of rTMS in the left DLPFC. The optimized stimulation intensity will be investigated by a pilot study. Changes in blood oxygenation that signal brain activity changes will be assessed using functional near-infrared spectroscopy (fNIRS) at rest and during engagement in several cognitive tasks. The findings from this study will (1) elucidate the optimal time interval between priming and test stimulation; (2) elucidate the influence of priming TBS on emotion discrimination as well as executive function and its underlying brain activity in subclinical depression; and (3) validate homeostatic metaplasticity in the left DLPFC.

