**4) Primary Disease or Condition being studied in the trial, or the focus of the study:**  
Subclinical Depression

**5) Keywords:** Priming Stimulation, Theta-Burst Stimulation, Functional NIRS, Emotion Discrimination, Subclinical depression

**6) Primary Purpose:** Optimization of stimulation parameters for a priming stimulation protocol

**7) Study Phase:** N/A

**8) Intervention Study Model:** Parallel, sham-control

**9) Model Description:** (Objectives)

The proposed research has two primary objectives.

The first objective is to understand the effects of priming stimulation timing of the left DLPFC using fNIRS at rest. The time window between priming cTBS and test iTBS will be either 0, 10, or 20 minutes. We hypothesize that 0 minutes will eliminate the effect of the test iTBS, whereas 10 minutes will potentiate it; 20 minutes will have no effect (i.e., result in no difference, relative to sham priming).

The second objective is to evaluate the effects of priming stimulation in the context of facial emotion processing and executive function in subclinical depression. Previous evidence indicates that DLPFC stimulation modulates affective processing on the neural and behavioral level. We hypothesize that optimal priming stimulation will affect reaction times in an emotion-specific way and will reduce the negative bias observed in subclinical depression.

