Hypothesis E2 will be supported if there is a significant interaction between time, emotion and conditions 2 and 1.

Hypothesis E3 will be supported if there is a significant interaction between time, emotion and conditions 3 and 1.

Hypothesis E4 will be supported if there is a significant change in condition 4 in some (e.g. sad) but not other emotions (e.g. happy) after stimulation (following a post-hoc 2-way interaction between time and emotion).

Finally, two t-tests comparing ERA- recognition accuracies between subclinically depressed and control participants and between pre and post stimulation in the sample of subclinically depressed participants will be performed in order to test hypotheses E5 and E6, respectively.

Hypothesis E5 will be supported if recognition accuracy is reduced in participants with subclinical depression compared to the control sample.

Hypothesis E6 will be supported if recognition accuracy will be increased after stimulation compared to baseline in participants with subclinical depression.

Behavioral data will be analyzed using the IBM SPSS software (<http://www-01.ibm.com/software/analytics/spss/>). The alpha level will be set at 0.05, adjusted for multiple comparisons using the Bonferroni-Holm procedure. For GLM, post-hoc pairwise comparisons will be corrected using Fisher least significant difference procedure in accordance with the closed test principle, i.e., post hoc comparisons will be declared nonsignificant if the global p value of the main- or interaction effect is nonsignificant, but carried out without further correction in case of a significant global effect.

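### Hypothesis 4 is counted as supported when the condition 1 versus 4 test is non-significant, so a missed difference is read as no difference

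*Combined protocol and SAP*

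**What the plan says.** Section 9 (Model Description) makes a null prediction for the longest interval: "20 minutes will have no effect (i.e., result in no difference, relative to sham priming". Section 13 tests it with two t-tests, one pre-post within condition 4 and one on change scores between conditions 1 and 4. Support requires "a significant increase in prefrontal HbO after stimulation, but no significant difference in change scores between condition 1 and 4".

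The 10-minute interval is handled by an ordinary superiority test: hypothesis 3 needs a "significant stronger change in HbO in condition 3 compared to condition 1". Section 2 states the purpose of these comparisons, which is to "elucidate the optimal time interval between priming and test stimulation".

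Section 10 gives "Number of Subjects: 80 participants with subclinical depression" in four arms. Section 13 sets alpha at 0.05, "adjusted for multiple comparisons using the Bonferroni-Holm procedure", without saying whether that covers the resting-HbO tests of hypotheses 1 to 4. The documents give no equivalence margin, confidence-interval criterion, SD, effect size or power figure.

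**The concern.** A non-significant t-test shows that the data did not exclude zero. It does not show that the difference is small. With a small arm it is the likely result even when the true difference is moderate, so the rule can confirm hypothesis 4 because the trial is imprecise.

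The first limb (a significant rise in condition 4) does not repair this. It compares condition 4 with its own baseline, not with sham priming. It protects when condition 4 barely responds. It does not protect when condition 4 clearly rises but differs moderately from condition 1, which includes the case where 20 minutes still potentiates.

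The stake is the timing conclusion. Hypothesis 4 is the only resting-HbO hypothesis about 20 minutes, and none of hypotheses 1 to 4 compares condition 3 with condition 4. A significant hypothesis 3 together with a supported hypothesis 4 would be read as a difference between 10 and 20 minutes that was never tested. Any multiplicity adjustment applied to the 1 versus 4 test would also make its non-significance easier to reach.

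A smaller point of the same kind: section 9 says "We hypothesize that 0 minutes will eliminate the effect of the test iTBS", but hypothesis 2 is supported by a "significant stronger change in HbO in condition 1 compared to condition 2". That test can show attenuation, not elimination.

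**Working it through.** **Inputs.** From the documents: 80 participants, four arms, alpha 0.05. Assumed, because the documents are silent: equal allocation (n = 80/4 = 20 per arm), no dropout, two-sided unadjusted tests, normal change scores with equal SD, and one prefrontal HbO value per participant. Effects are in units of the change-score SD. The plan states no power or margin, so there is no figure of its own to reproduce.

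**Second limb alone.** The two-sample t-test has 38 df and noncentrality d × √(n/2) = d × √10. At d = 0.5 this is 1.58, against a critical value of 2.02. From the noncentral t distribution:

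| True difference (SD) | P(non-significant) |
|---|---|
| 0.3 | 85% |
| 0.5 | 66% |
| 0.8 | 31% |

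The probability of passing falls below one half only above 0.64 SD. The 95% CI half-width for the difference is t(0.975, 38) × √(2/20) = 2.024 × 0.316 = 0.64 SD.

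**Full two-limb rule.** Simulated probability that condition 4 rises significantly and the 1 versus 4 test is non-significant:

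| True mean change, condition 1 / condition 4 | Difference (4 minus 1) | Hypothesis 4 supported |
|---|---|---|
| 0.8 / 0.8 | 0 | 89% |
| 0.8 / 1.3 | +0.5 | 66% |
| 0.5 / 1.0 | +0.5 | 65% |
| 0.3 / 0.8 | +0.5 | 59% |
| 0.2 / 0.7 | +0.5 | 51% |
| 0 / 0.5 | +0.5 | 27% |
| 0.8 / 1.6 | +0.8 | 31% |
| 1.3 / 0.8 | −0.5 | 65% |
| 1.0 / 0.5 | −0.5 | 47% |
| 0.8 / 0.3 | −0.5 | 23% |
| 0.5 / 0 | −0.5 | 2% |

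**Effect of sample size.** At 0.8 / 1.3, support falls as the arms grow: 77% at 10 per arm, 73.5% at 15, 66% at 20 and 40% at 40.

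**Effect of a stricter alpha.** With both limbs at 0.01 (the first Holm step for five tests), support at 20 per arm is 61% for 0.3 / 0.8 and 79% for 0.5 / 1.0, against 59% and 65% at 0.05.

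**False timing contrast.** Let conditions 3 and 4 be identical, both 0.5 SD above sham priming (1.3 versus 0.8). Hypothesis 3 is significant in 34% of trials, and hypotheses 3 and 4 are both declared supported in 15% of all trials, which is 45% of those with a significant hypothesis 3. If both intervals exceed sham priming by 0.8 SD (1.6 versus 0.8), the figures are 69%, 14.5% and 21%.

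**The case against.** The percentages depend on effect sizes the documents do not give. About 6 in 10 requires condition 4 to rise by roughly 0.8 SD or more. For the same 0.5 SD excess over sham priming, smaller rises give 51% (0.2 / 0.7), 40% (0.1 / 0.6) and 27% (0 / 0.5), because the first limb then often fails. This stands, and the headline figure is limited to a clear rise.

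It is also not general that fewer participants make support easier. At 0.3 / 0.8 the rule passes in 44% of trials at 10 per arm, 56% at 15, 59% at 20 and 40% at 40. This stands too; the steady fall belongs to scenarios where condition 4 rises strongly.

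The false timing pattern is better judged by its overall frequency, about one trial in seven, than by the 45% conditional figure. That is fair.

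Section 13 determines HbO changes for each of 52 channels and does not say how they are combined for hypotheses 1 to 4. If the limbs were judged by channel, the percentages would change. Section 3 refers to a separate proposal that is not available here and might discuss margins or power.

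None of these points repairs the rule. Under every way of combining channels it still treats failure to reject as evidence of no difference, and nothing in the two documents sets another criterion.

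**Conclusion.** The concern holds. The success rule for hypothesis 4 is wrong as written: its second limb cannot support a claim of no difference. At 20 per arm and two-sided alpha 0.05, with one HbO summary per participant, a condition 4 that clearly rises and exceeds sham priming by 0.5 SD is still declared in line with hypothesis 4 in 59% to 66% of trials. If 10 and 20 minutes are equally effective, at 0.5 or 0.8 SD above a sham-priming change of 0.8 SD, about 15% of trials would report that only 10 minutes potentiates. The sizes rest on the stated assumptions; the logical error does not. Hypotheses 1 to 3 are unaffected as superiority tests, apart from the wording of the hypothesis 2 conclusion. This should be fixed before the data are compared by condition.

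**What to change.** In section 13, replace the hypothesis 4 criterion with text such as:

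> For hypothesis 4 we report the condition 4 minus condition 1 difference in mean HbO change with its 95% CI, alongside the condition 4 pre-post test. A non-significant difference is inconclusive and does not support hypothesis 4. No difference is claimed only if the 90% CI lies inside a margin justified and fixed before the data are compared by condition.

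If no margin can be justified, omit the last sentence. Base any statement that 10 minutes works and 20 does not on the condition 3 minus condition 4 difference with its CI. State which tests the Holm procedure covers, and do not use it to make a no-difference claim easier. Word the hypothesis 2 conclusion as attenuation.

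The cost is SAP text and one added contrast on data already collected. The price is that hypothesis 4 will often be inconclusive. An equivalence test (two one-sided tests at 5%) at 20 per arm performs as follows:

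| Margin (SD) | Declared equivalent, true difference 0 | Declared equivalent, true difference 0.5 SD |
|---|---|---|
| 0.5 | 3% | 1% |
| 0.8 | 60% | 23% |
| 0.95 | 81% | 40% |

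A wide margin therefore brings the problem back. A 0.5 SD margin would need about 70 per arm for 80% power at a true difference of zero.

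### For resting HbO, Section 13 lets only the 10-minute interval be concluded larger than sham priming, and it has no rule for choosing the optimal interval

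*Combined protocol and SAP*

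**What the plan says.** The Brief Summary says that the findings will "elucidate the optimal time interval between priming and test stimulation". Item 6 gives the primary purpose as "Optimization of stimulation parameters for a priming stimulation protocol". Item 9 lists the candidates: "The time window between priming cTBS and test iTBS will be either 0, 10, or 20 minutes". It also gives one prediction per interval: "We hypothesize that 0 minutes will eliminate the effect of the test iTBS, whereas 10 minutes will potentiate it", with 20 minutes expected to match sham priming.

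Section 13 turns these predictions into support rules:

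- **Hypothesis 2 (0 minutes):** "Hypothesis 2 will be supported if there is a significant stronger change in HbO in condition 1 compared to condition 2".
- **Hypothesis 3 (10 minutes):** supported by "a significant stronger change in HbO in condition 3 compared to condition 1".
- **Hypothesis 4 (20 minutes):** supported by a significant pre-post increase in condition 4, "but no significant difference in change scores between condition 1 and 4".

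Hypothesis 1 is a pre-post test within the sham-priming arm. Section 13 does not label Hypotheses 1 to 4 as resting analyses. That reading follows from the first objective in item 9, from the primary outcome in item 11, and from the assignment of task HbO and behaviour to the exploratory hypotheses. The mixed models with pairwise comparisons between conditions belong to those exploratory hypotheses. For resting HbO there is no omnibus test, no contrast between active intervals and no selection rule.

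**The concern.** The trial exists to choose an interval, and the Brief Summary itself says that systematic studies of the timing are lacking. The support rules nevertheless fix in advance which interval may be found potentiating. If the prediction is right, Hypothesis 3 can confirm it. If 0 or 20 minutes is truly better, the evidence would come from a planned test, but the plan does not say what that result means for the interval. The conclusion would then have to be written after the data are seen.

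Two further weaknesses concern 20 minutes. Hypothesis 4 goes unsupported whether that interval is better than sham, worse than sham, or merely misses the pre-post limb, so the label says little. It can also be supported because a small comparison was not significant, which is not evidence of no difference. Finally, even when Hypothesis 3 is supported, 10 minutes has not been compared with 0 or 20 minutes, so nothing in the rules establishes it as optimal.

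**Working it through.** **Reading the rules.** Each active arm's change score is compared with condition 1. The table shows what Section 13 concludes for each possible result.

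| Arm | Significantly larger than sham | Not significant | Significantly smaller than sham |
|---|---|---|---|
| 0 min | H2 not supported | H2 not supported | H2 supported |
| 10 min | H3 supported | H3 not supported | H3 not supported |
| 20 min | H4 not supported | H4 supported if the pre-post limb passes | H4 not supported |

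A larger change than sham leads to a positive conclusion in one row only. This follows from the wording and needs no numbers.

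**Inputs for the illustration.** The plan gives no power, SD or effect size, so there is no figure to reproduce. From item 10: "Number of Subjects: 80 participants with subclinical depression" in four arms. Assumed: equal allocation, so 80/4 = 20 per arm; change-score SD 1; two-sided 0.05 (sidedness is not stated); effects over a range.

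**Single contrast with sham.** The standard error is √(2/20) = 0.316 SD. The noncentrality is d × √(20/2) = 3.162d, with 38 df. The critical t is 2.024 unadjusted and 2.505 at 0.05/3 (first Holm step). For Dunnett with three contrasts and 76 df it is 2.397.

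| True gain d | Noncentrality | Unadjusted | Holm, first step | Dunnett |
|---|---|---|---|---|
| 0.8 | 2.530 | 69% | 52% | 55% |
| 1.0 | 3.162 | 87% | 74% | 78% |

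At d = 0.5 (noncentrality 1.581) the figures are 34% unadjusted and 19% with Holm.

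If 20 minutes is the only interval that helps, the unadjusted column is how often its planned test would be significantly positive. Each such result is recorded only as H4 not supported. With 10 minutes adding nothing, H3 is supported in about 2.5% of trials.

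**What H4 not supported covers** (simulation, unadjusted tests, iTBS effect 0.5 SD in the sham arm):

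- 20 minutes adds 0.8 SD: about 70% of trials.
- 20 minutes subtracts 0.8 SD: about 100% (98% if the iTBS effect is 0.8 SD).
- 20 minutes adds nothing: 46% (77% or 11% if the iTBS effect is 0.3 or 0.8 SD).

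**How often H4 is supported when it is false.** With an iTBS effect of 0.8 SD and a true gain of 0.8 SD at 20 minutes, H4 is supported in 31% of trials unadjusted and in 48% with Holm. With a true gain of 0.5 SD the figures are 66% and 81%. Stricter adjustment makes this support easier to obtain. The 95% half-width for a contrast is 2.024 × 0.316 = 0.64 SD, so a non-significant result can leave a sizeable gain or loss open.

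**Whether testing against sham is enough.** If 10 minutes adds 0.8 SD and 20 minutes adds 1.0 SD, both beat sham under Holm in 52% of trials. A rule limited to contrasts with sham then names no winner, so a selection step is needed. Choosing the larger mean is fallible: the expected difference is 0.2 SD with standard error 0.316, and 0.2/0.316 = 0.63, so the wrong interval has the larger mean in about 26% of trials.

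**The case against.** Directional predictions are legitimate, and support rules that mirror them are ordinary practice. The tests of condition 2 and condition 4 against condition 1 are already planned, so a two-sided result in the unexpected direction would be visible with its sign. Section 13 states when a hypothesis is supported and does not restrict what else may be reported. The detailed description is left to a proposal that is not part of these documents and may contain a selection rule.

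Most of this stands, and it rules out stronger readings. A reader might infer that the plan can return only potentiation at 10 minutes or nothing. It cannot be read so: it can also return an iTBS effect in the sham arm, attenuation at 0 minutes, and its own no-difference conclusion at 20 minutes. A reader might also infer that a benefit at 20 minutes would be hidden, or reported as failure of priming. The documents say neither. It would also be wrong to set the 69% beside the 52% as if the present rules detected more: the first is unadjusted and the second uses Holm.

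What the objection does not supply is the missing rule. Given the stated aim of finding the optimal interval, visibility of an unexpected sign is not a pre-specified conclusion. If the tests were one-sided in the predicted direction, a larger change at 0 minutes would not be flagged at all.

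**Conclusion.** The concern holds in a limited form. For resting HbO, Section 13 lacks a pre-specified conclusion for a larger change than sham at 0 or 20 minutes, lacks a way to choose among intervals, and treats non-significance at 20 minutes as support for no difference. The analyses largely exist; the rules that turn them into an answer about the interval do not.

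The finding rests on the wording of the rules. The percentages only show scale, and they depend on equal allocation, SD 1, two-sided tests and the assumed effects. Confidence is medium, because the referenced proposal could not be seen. The text should be changed before unblinded data are analysed, but the point does not invalidate the design.

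**What to change.** In Section 13, for resting HbO:

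1. Test the change in conditions 2, 3 and 4 against condition 1, each two-sided.
2. Adjust the three contrasts together, by Holm or by step-down Dunnett from one four-arm model, and state that this adjustment covers resting HbO. The present Bonferroni-Holm sentence follows one on behavioural data, so its reach is unclear.
3. Apply one reading to all three: significantly larger is potentiation, significantly smaller is attenuation, anything else is inconclusive.
4. Keep Hypotheses 2 and 3 as directional predictions. Report a non-significant result for condition 4 with its confidence interval, and not as support for Hypothesis 4.
5. Among intervals declared potentiating, name the one with the largest mean change as the candidate optimum, and report the between-interval differences with confidence intervals. The word candidate matters, because close intervals will often not be separable at this sample size.

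The cost is SAP wording and some shared alpha, with no added participants or measurements. With 20 per arm and SD 1, if the primary tests would otherwise be unadjusted, power for Hypothesis 3 alone at 0.8 SD falls from about 69% to about 52% (Holm) or 55% (Dunnett, which assumes a common variance across arms). If the existing Holm rule already covers these contrasts, there is little or no loss. Hypothesis 4 can no longer be supported by non-significance alone.
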